5.3 Concomitant Medications

Carfilzomib is primarily metabolized via peptidase and epoxide hydrolase activities, therefore the pharmacokinetics (PK) profile of carfilzomib should not be affected by concomitant administration of cytochrome P450 (CYP) inhibitors and inducers. Carfilzomib is not expected to influence exposure of other drugs. However, patients will be instructed not to take any additional medications during the course of the study without prior consultation with the research team. At each visit, the patient will be asked about any new medications he is taking or has taken after the start of the study drug.

CONFIDENTIAL

STUDY DRUG(S): CARFILZOMIB AMENDMENT 2 DATE: 25 FEBRUARY 2015

5.3.1 Permitted Concomitant Medications

Premedication with anti-emetics should be given according to institutional practice.

Medications may be administered for maintenance of existing conditions prior to study enrollment, or for a new condition that develops while on study, including but not limited to the following:

- Allopurinol (or other approved uric acid-lowering agent) in patients at high risk for TLS due to high tumor burden may be prescribed at the investigator's discretion.
- Prophylactic antiviral therapy (e.g., valacyclovir) per institutional standard practice is strongly recommended for patients at increased risk of herpes zoster.
- Patients may receive antiemetics and antidiarrheal agents as necessary.
- Myeloid growth factors (e.g., granulocyte-colony stimulating factor [G-CSF]) may be used if neutropenia occurs in accordance with American Society of Clinical Oncology (ASCO) Guidelines (Smith et al. 2006), but should not be given prophylactically.
- Patients may receive RBC transfusions, erythropoietic stimulating agents, or platelet transfusions at any time.
- Palliative radiation for pain management is permitted with the written approval of the Study Chair. The radiation field cannot encompass a target lesion.

Other medications considered necessary for the patient's safety and well-being may be given at the discretion of the investigator with the exception of those listed in Section 5.3.2.

5.3.2 Prohibited Concomitant Medications

The following treatments are prohibited while in this study:

- No other investigational therapy should be given to patients. No anticancer agents other than the study medications should be given to patients. If such agents are required for a patient, then the patient must first be withdrawn from the study.
- Herbal preparations/medications are not allowed throughout the study. These herbal medications include, but are not limited to: St. John's wort, kava, ephedra (ma huang), gingko biloba, dehydroepiandrosterone (DHEA), yohimbe, saw palmetto, and ginseng. Patients should stop using these herbal medications 7 days prior to first dose of study drug.

5.4 Correlative Studies

5.4.1 Tumor Tissue Samples

Archival tumor samples may be collected during the study with the purpose of identifying molecular alterations relevant to carfilzomib.

6. **DOSE MODIFICATIONS**

If toxicity occurs, the toxicity will be graded utilizing the NCI CTCAE v4.03 (https://evs.nci.nih.gov/ftp1/CTCAE/CTCAE), and appropriate supportive care treatment will be administered to decrease the signs and symptoms thereof. Dose adjustments will be based on the organ system exhibiting the greatest degree of toxicity.

CONFIDENTIAL

STUDY DRUG(S): CARFILZOMIB AMENDMENT 2 DATE: 25 FEBRUARY 2015

Doses of carfilzomib will be modified based on hematologic and non-hematologic toxicity. If dose reductions are necessary, they will be permanent for the remainder of the treatment. Carfilzomib may be adjusted according to the dose modification tables that follow. If the patient is receiving the lowest allowable dose and experiences a toxicity requiring a dose reduction, the offending study drug should be discontinued. Any patient requiring a toxicity-related dose delay of more than 21 days from the intended day of the next scheduled dose must be discontinued from the study.

If patients experience any dose-related toxicity at 20 mg/m^2 , they must be discontinued from the study.

A maximum of two dose reductions are allowed in this study. If more than two dose reductions are necessary for a patient, the patient will be discontinued from study treatment.

The dose level reductions to be used in this study are presented in Table 2.

Dose Level	Carfilzomib
Starting Dose	56 mg/m^2
Dose Level -1	45 mg/m ²
Dose Level -2	36 mg/m ²

Table 2Dose Level Modifications

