DRUG	DOSE	CYCLE	FREQUENCY	Route of Administration
Carfilzomib ^{a, c}	20 mg/m ²	Cycle 1 only	Days 1, 2	IV over 30 minutes
Carfilzomib ^a	filzomib ^a 56 mg/m ² Cycle 1 only Days 8, 9, 15		Days 8, 9, 15, 16	IV over 30 minutes
Carfilzomib ^{b, c}	56 mg/m^2	Cycle 2 and beyond	Days 1, 2, 8, 9, 15, 16	IV over 30 minutes

Table 1Overall Treatment Plan

^a Carfilzomib 20 mg/m² IV will be infused over 30 minutes (\pm 5 minutes) on Days 1 and 2 of Cycle 1, followed by escalation to 56 mg/m² infused over 30 minutes (\pm 5 minutes) on Days 8, 9, 15, and 16 of Cycle 1.

^b Carfilzomib 56 mg/m² IV will be infused over 30 minutes (\pm 5 minutes) on Days 1, 2, 8, 9, 15, and 16 of Cycle 2 and beyond.

 $^{\rm c}$ Study drug will be taken within $\pm\,2$ days of the scheduled study day for Day 1 of each Cycle.

Carfilzomib will be administered within ± 2 days of the scheduled study day for Day 1 of each Cycle. Every effort should be made to maintain the dosing schedule as outlined above, and if this is not possible due to extenuating circumstances then priority should be given to maintain consecutive dosing days. If a mid-cycle dose is missed, that dose should be administered no more than 2 days after the scheduled dosing day. Anticipated treatment changes outside of the 2-day window must be discussed with the Medical Monitor or designee.

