6.1 Dose Modifications Due to Hematologic Toxicity

If hematologic toxicity occurs, hold all study drugs and re-evaluate in 1 week. Absolute neutrophil count (ANC) and platelets should be monitored weekly until recovery. If ANC and/or platelets do not recover within 3 weeks, the patient will be discontinued from the study.

Dose modifications on Day 1 of each cycle will be based on blood counts determined on the day of scheduled treatment. Nadir blood counts will not be used to determine dose modifications. Dose reductions for hematological toxicities are show in Table 3.

CONFIDENTIAL

AE Term and Description	Dose Modification	
THROMBOCYTOPENIA		
Grade 3 (25 - <50 x 10 ⁹ /L)	1. Interrupt study treatment until toxicity reduced to \leq Grade 2 ^a .	
	 If improves in ≤ 7 days, maintain same dose, if > 7 days reduce dose 1 level. 	
Grade 4 (<25 x 10 ⁹ /L)	 Interrupt study treatment until toxicity reduced to ≤ Grade 2^a. 	
	2. Restart treatment with a 1 level dose-reduction.	
Recurrent Grade 3/4 Event After Initial Dose Reduction	1. Interrupt study treatment until toxicity reduced to \leq Grade 2 ^a .	
	2. Restart treatment with a second 1 level dose-reduction.	
Recurrent Grade 3/4 Event After 2 Dose Reductions	Discontinue	
NEUTROPENIA		
Grade 3 ($0.5 \ge 10^9/L \le ANC < 1.0 \ge 10^9/L$)	 Interrupt study treatment until toxicity reduced to ≤ Grade 2^a. 	
	 If improves in ≤ 7 days, maintain same dose, if >7 days reduce dose 1 level. 	
Grade 4 (ANC <0.5 x 10 ⁹ /L)	 Interrupt study treatment until toxicity reduced to ≤ Grade 2^a. 	
	2. Restart treatment with a 1 level dose-reduction.	
Recurrent Grade 3/4 Event After Initial Dose Reduction	 Interrupt study treatment until toxicity reduced to ≤ Grade 2^a. 	
	2. Restart treatment with a 1 level dose-reduction.	
Recurrent Grade 3/4 Event After 2 Dose Reductions	Interrupt until toxicity \leq Grade ^{2a} and restart treatment with a 1 level dose-reduction if possible, or discontinue.	

Table 3 Carfilzomib Dose Modifications for Hematologic Toxicities

a Hold carfilzomib treatment; do at least weekly CBC with differential until toxicity resolves (ANC recovery $\ge 1.0 \times 10^{9}$ /L and platelets $\ge 75 \times 10^{9}$ /L).

b Re-treatment criteria = ANC recovery $\geq 1.0 \times 10^9$ /L and platelets $\geq 75 \times 10^9$ /L.

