6.2 Dose Modifications for Non-Hematologic Toxicity

The dose reduction guidelines for non-hematologic toxicities are shown in Table 4.

CONFIDENTIAL

Table 4	Carfilzomib Dose Reductions for Grade 3 or 4 Non-Hematologic Toxicities
---------	--

Event	Action to be Taken
Allergic reaction/hypersensitivity Grade 2 – 3 Grade 4	Hold until ≤ Grade 1, reinstitute at full dose. Discontinue
Tumor lysis syndrome	
$(\geq 3 \text{ of following:} \geq 50\% \text{ increase in creatinine,} uric acid, or phosphate; \geq 30\% increase in potassium; \geq 20\% decrease in calcium; or \geq 2-fold increase in LDH$	Hold carfilzomib until all abnormalities in serum chemistries have resolved. Reinstitute at full doses.
Infection Grade 3 or 4	Hold carfilzomib (no more than 3 weeks) until systemic treatment for infection complete. If no neutropenia, restart at full dose. If neutropenic, follow neutropenic instructions (Table 3).
Herpes zoster or simplex of any grade	Hold carfilzomib until lesions are dry. Reinstitute at full dose.
Neuropathy	
Grade 2 treatment emergent neuropathy with pain or Grade 3 neuropathy	Continue to dose. If neuropathy persists for more than two weeks hold carfilzomib until resolved to \leq Grade 2 without pain. Then restart at 1 dose decrement.
Grade 4 neuropathy	Discontinue carfilzomib
Renal Dysfunction	Please refer to Table 5.
Congestive heart failure	Any patient with symptomatic congestive heart failure, whether or not drug related, must have the dose held until resolution or return to baseline, after which treatment may continue at a reduced dose, or the patient may be withdrawn from the study. If no resolution after 2 weeks, the patient will be withdrawn from the study.
Other non-hematologic toxicity assessed as carfilzomib-related \geq Grade 3	Hold dose until toxicity resolves to \leq Grade 1 or baseline. Restart at 1 dose decrement.

a Carfilzomib should be held until toxicity resolves to \leq Grade 1. Patients who develop irreversible Grade 3/4 non-hematologic toxicity, or toxicity that does not resolve to \leq Grade 1 within 3 weeks, should be removed from the study.

b No more than 2 dose reductions of carfilzomib are allowed.

CONFIDENTIAL

STUDY DRUG(S): CARFILZOMIB AMENDMENT 2 DATE: 25 FEBRUARY 2015

Renal Dysfunction	Recommended Action
\geq 0 and < 25% decrease in CrCl over baseline	Based on investigator judgment; no dose modification may be necessary.

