\geq 25% and < 50% decrease in CrCl over baseline	Hold carfilzomib dose until CrCl is stable. If attributable to carfilzomib, resume carfilzomib at one dose decrement. If not attributable to carfilzomib, restart at dose used prior to the event.
≥ 50% decrease in CrCl over baseline or CrCl < 15 mL/minute (NCI-CTC Grade 4)	 Hold carfilzomib dose until CrCl improves to < 25% decrease over baseline and CrCl returns to ≥ 15 mL/ minute (if CrCl dropped to < 15 ml/min). If attributable to carfilzomib, resume carfilzomib at one dose decrement. If not attributable to carfilzomib, restart at dose used prior to the event. If dialysis is required, may resume at a maximal dose of 20 mg/m2 and administer the carfilzomib after dialysis.

Table 5Recommended Action for Renal Dysfunction

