8.1.3 Infusion reaction

Infusion reactions associated with IV administration of carfilzomib were characterized by a spectrum of systemic symptoms including fever, chills, arthralgia, myalgia, facial flushing, facial edema, vomiting, weakness, shortness of breath, hypotension, syncope, chest tightness, or angina. These reactions can occur immediately or up to 24 hours after administration. Administration of dexamethasone prior to carfilzomib dosing reduce the incidence and severity of reactions. Inform patients of symptoms and ask them to contact physician if symptoms of an infusion reaction occur. Infusion reactions should be treated as per institutional protocol.

Infusion reactions (e.g., rash, urticaria, erythema, pruritus, bronchospasm, and hypotension) can occur with the agent used in this study. To identify the grade of a reaction, refer to the list below adapted from the General Disorders and Administration Site Conditions section of the NCI CTCAE v 4.03:

- Grade 1: Mild transient reaction; infusion interruption not indicated; intervention not indicated.
- Grade 2: Therapy or infusion interruption indicated but responds promptly to symptomatic treatment (e.g., antihistamines, NSAIDs, narcotics, IV fluids indicated for ≤24 hours).
- Grade 3: Prolonged (e.g., not rapidly responsive to symptomatic mediation and/or brief interruption of infusion); recurrence of symptoms following initial improvement; hospitalization indicated for other clinical sequelae. Note: any infusion that is interrupted and not resumed within the visit will be considered a Grade 3 reaction.
- Grade 4: Life-threatening consequences; urgent intervention indicated.

Minor symptoms such as flushing, skin reactions, dyspnoea, lower back pain, hypotension, or tachycardia may require temporary interruption of the infusion. However, severe reactions, such as hypotension requiring treatment, dyspnoea requiring bronchodilators, angioedema or generalized urticaria may require immediate treatment discontinuation and aggressive symptomatic therapy. Patients who experience a severe reaction should not be re-challenged.

CONFIDENTIAL

STUDY DRUG(S): CARFILZOMIB AMENDMENT 2 DATE: 25 FEBRUARY 2015

Patients who experience an allergic/infusion reaction may be pre-medicated for subsequent cycles per local guidelines and clinical practice.

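### Section 6 orders study removal for any dose-related toxicity at 20 mg/m², with no grade, although every patient starts at that dose and other rules would keep some of the same patients

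*Combined protocol and SAP*

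**What the plan says.** The opening text of Section 6 contains three relevant statements.

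- The tables are introduced permissively: "Carfilzomib may be adjusted according to the dose modification tables that follow".
- A patient who is "receiving the lowest allowable dose and experiences a toxicity requiring a dose reduction" stops the drug.
- A separate sentence begins "If patients experience any dose-related toxicity at" 20 mg/m² and makes leaving the study mandatory. It carries no grade, no cycle limit and no definition of dose-related.

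Section 5 and Table 1 give every patient 20 mg/m² on Cycle 1 Days 1 and 2, with escalation to 56 mg/m² from Day 8. Table 2 lists 56, 45 and 36 mg/m²; 20 mg/m² is not a reduction level.

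Other rules manage toxicity by grade and do not exempt the first two doses:

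- Table 3, Grade 3 thrombocytopenia or neutropenia: hold; if the count improves within 7 days, "maintain same dose, if > 7 days reduce dose 1 level".
- Table 4: a Grade 2–3 allergic reaction or tumor lysis syndrome is held until recovery and restarted at full dose. Some other rows say "restart at 1 dose decrement".
- Table 5: patients needing dialysis "may resume at a maximal dose of 20 mg/m2".
- Section 8.1.3: "Patients who experience a severe reaction should not be re-challenged", while patients with other allergic or infusion reactions may be premedicated and continue.
- Section 3.3: among toxicities, those that are irreversible or intolerable, or laboratory abnormalities attributed to the drug, lead to stopping treatment.

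**The concern.** Followed to the letter, the Section 6 sentence ends participation for a mild reaction on Day 1 that the rest of the protocol expects sites to manage. Dexamethasone premedication in Cycle 1 is there to lessen such reactions. A site that follows the tables instead keeps the patient. Both sites can say they followed the protocol, because nothing states which rule prevails.

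What is at stake is first whether a patient stays on a potentially useful drug, and whether sites treat like cases alike. The primary endpoint is also touched. A patient removed after one or two doses stays in the Full Analysis Set (Section 10.3) if disease was measurable at baseline. Without a post-baseline scan, that patient is a non-responder for ORR (Section 10.4.1). The same patient drops out of the Evaluable Population, which requires two full cycles.

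**Working it through.** The plan gives no figure on this point, so the check compares rules. Take an event that a site judges dose-related and that arises when only 20 mg/m² has been given. Section 6, read literally, removes the patient in every row below.

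| Event | Rule elsewhere | Agrees with literal Section 6? |
|---|---|---|
| Mild event with no action in Tables 3–5 | Continue | No |
| Non-severe infusion reaction | 8.1.3: may premedicate and continue | No |
| Grade 2 allergic reaction | Table 4: hold, then full dose | No |
| Tumor lysis syndrome | Table 4: hold, then full dose | No |
| Grade 3 cytopenia improving within 7 days | Table 3: hold, then same dose | No, if a Day 8 count is used |
| Grade 3 allergic reaction | Table 4: full dose; 8.1.3: no re-challenge if severe | Unclear; these two rules also disagree |
| Grade 3 cytopenia lasting over 7 days, Grade 4 cytopenia, febrile neutropenia | Table 3: reduce one level | Yes in effect; no lower level exists |
| Other related non-hematologic toxicity, Grade 3 or higher | Table 4: reduce one level | Yes in effect; no lower level exists |
| Grade 4 allergic reaction or neuropathy | Table 4: discontinue | Yes |

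The cytopenia row is conditional. Section 7.3.1 calls for a blood count on Day 8, up to 72 hours before treatment, and on the planned schedule that count follows 20 mg/m² doses only. Section 6.1, however, says nadir counts do not determine dose modifications, so it is arguable whether a Day 8 count may trigger Table 3. The allergic-reaction, tumor-lysis and mild-event rows do not depend on this.

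Two coherent readings of the sentence are available:

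- Reading A: it works like the lowest-dose rule, so only toxicity requiring a reduction leads to removal.
- Reading B: the mandatory sentence overrides the permissive tables, so any dose-related toxicity leads to removal.

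They agree wherever a row requires a reduction or discontinuation. They differ for same-dose and full-dose rows and for events that need no action. The text does not choose between them.

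The design in Section 10.2 was checked to see whether any stated figure is affected. Stage 1 has 23 patients and continues with at least 2 responses; stage 2 adds 33; rejection needs at least 6 of 56. The rejection probability is the sum over x = 2 to 23 of P(X = x) × P(Y ≥ 6 − x), with X ~ Bin(23, p) and Y ~ Bin(33, p). At p = 0.05 this is 0.04996; at p = 0.15 it is 0.8003. Both match the stated 0.05 and 80%.

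**The case against.** The best defense is that a specific mandatory sentence prevails over tables that are only permissive, and that the sponsor may have wanted a hard stop: a patient who reacts to 20 mg/m² should not receive 56 mg/m² a week later. That intent is possible and has to be asked about. But the protocol does not state it, and it would make several table rows inoperative for toxicity at 20 mg/m². It also fits poorly with Section 8.1.3, which reserves the ban on re-challenge for severe reactions.

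A second defense is that the sentence only restates the lowest-dose rule, or targets the dialysis row of Table 5. Either is plausible, but its wording is limited to neither.

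Two stronger readings should be resisted.

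- A reader might infer that a patient with a reduction-type toxicity at 20 mg/m² would be restarted at 45 mg/m², above the dose that caused it. That would require a site to ignore the mandatory sentence and apply a ladder that starts at 56 mg/m². Readings A and B both discontinue this patient.
- A reader might infer that the trial's power is below 80%. The documents give no rate of toxicity after Days 1 and 2. If the 15% alternative already describes all treated patients, with early removals counted as non-responders, power does not change. Counting such patients as non-responders is the plan's own rule, not an error. Patients needing a reduction would also still leave under a corrected rule, so a comparison of removing all with removing none would not measure this defect.

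**Conclusion.** The sentence is wrong as written. It applies to every treated patient, has no severity threshold, and literally removes patients whom Tables 3 and 4 and Sections 3.3 and 8.1.3 would keep. The real disagreement is confined to mild events and to rows that allow a restart at the same or full dose; the cytopenia case depends on whether Day 8 counts are used. No stated design figure is wrong. Early removal will generally add a non-responder to the primary analysis, but how often this would happen cannot be estimated from the documents. The conclusion assumes that an any-grade stop was not intended, which only the sponsor can confirm.

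**What to change.** Replace the Section 6 sentence with:

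> If a toxicity at 20 mg/m² requires a dose reduction under Tables 3–5, the patient is discontinued, because no lower dose level exists. Otherwise the patient is managed by Tables 3–5 and, after recovery, resumes the Table 1 schedule; patients on dialysis stay at no more than 20 mg/m² (Table 5). Section 8.1.3 overrides Table 4: patients with a severe (Grade 3 or higher) infusion or hypersensitivity reaction are not re-challenged.

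The last sentence also settles the disagreement between Table 4 and Section 8.1.3 over Grade 3 reactions. Section 8.1.3 does not tie severe to a grade, so the Grade 3 threshold is a proposal to confirm.

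The medical monitor should first confirm the intent. If an any-grade stop was meant, keep the rule, define dose-related, and state that it overrides Tables 3–5.

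The cost is a short amendment with IRB review and no added visits or tests; adverse events, blood counts and chemistry are already assessed on Days 1, 8 and 15. The downside is that some patients with milder toxicity after Days 1 and 2, who would leave under the literal sentence, will go on to 56 mg/m².

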6.1 Dose Modifications Due to Hematologic Toxicity

If hematologic toxicity occurs, hold all study drugs and re-evaluate in 1 week. Absolute neutrophil count (ANC) and platelets should be monitored weekly until recovery. If ANC and/or platelets do not recover within 3 weeks, the patient will be discontinued from the study.

Dose modifications on Day 1 of each cycle will be based on blood counts determined on the day of scheduled treatment. Nadir blood counts will not be used to determine dose modifications. Dose reductions for hematological toxicities are show in Table 3.

CONFIDENTIAL

AE Term and Description	Dose Modification	
THROMBOCYTOPENIA		
Grade 3 (25 - <50 x 10 ⁹ /L)	1. Interrupt study treatment until toxicity reduced to \leq Grade 2 ^a .	
	 If improves in ≤ 7 days, maintain same dose, if > 7 days reduce dose 1 level. 	
Grade 4 (<25 x 10 ⁹ /L)	 Interrupt study treatment until toxicity reduced to ≤ Grade 2^a. 	
	2. Restart treatment with a 1 level dose-reduction.	
Recurrent Grade 3/4 Event After Initial Dose Reduction	1. Interrupt study treatment until toxicity reduced to \leq Grade 2 ^a .	
	2. Restart treatment with a second 1 level dose-reduction.	
Recurrent Grade 3/4 Event After 2 Dose Reductions	Discontinue	
NEUTROPENIA		
Grade 3 ($0.5 \ge 10^9/L \le ANC < 1.0 \ge 10^9/L$)	 Interrupt study treatment until toxicity reduced to ≤ Grade 2^a. 	
	 If improves in ≤ 7 days, maintain same dose, if >7 days reduce dose 1 level. 	
Grade 4 (ANC <0.5 x 10 ⁹ /L)	 Interrupt study treatment until toxicity reduced to ≤ Grade 2^a. 	
	2. Restart treatment with a 1 level dose-reduction.	
Recurrent Grade 3/4 Event After Initial Dose Reduction	 Interrupt study treatment until toxicity reduced to ≤ Grade 2^a. 	
	2. Restart treatment with a 1 level dose-reduction.	
Recurrent Grade 3/4 Event After 2 Dose Reductions	Interrupt until toxicity \leq Grade ^{2a} and restart treatment with a 1 level dose-reduction if possible, or discontinue.	

Table 3 Carfilzomib Dose Modifications for Hematologic Toxicities

a Hold carfilzomib treatment; do at least weekly CBC with differential until toxicity resolves (ANC recovery $\ge 1.0 \times 10^{9}$ /L and platelets $\ge 75 \times 10^{9}$ /L).

b Re-treatment criteria = ANC recovery $\geq 1.0 \times 10^9$ /L and platelets $\geq 75 \times 10^9$ /L.

c Patients who require a treatment delay of more than 3 weeks due to treatment-related toxicity will be discontinued from study treatment, unless the treating physician and the Study Chair agree that continued treatment at lower doses is in the best interest of the patient.

CONFIDENTIAL

STUDY DRUG(S): CARFILZOMIB AMENDMENT 2 DATE: 25 FEBRUARY 2015

Table 3Carfilzomib Dose Modifications for Hematologic Toxicities (continued)

AE Term and Description	Dose Modification
FEBRILE NEUTROPENIA	
Grade 3 ANC <1.0 x $10^9/L$, fever $\ge 38.5^{\circ}C$	 Interrupt study treatment until ANC recovery to ≤ Grade 2^a (ANC ≥ 1.0 x 10⁹/L) and resolution of fever <38.5°C. Restart treatment with a 1 level dose- reduction.
Grade 4 ANC <1.0 x 10^{9} /L, fever \geq 38.5°C and life- threatening consequences	 Interrupt study treatment until ANC recovery to ≤ Grade 2^a (ANC ≥ 1.0 x 10⁹/L) and resolution of fever <38.5°C and any complications. Restart treatment with a 1 level dose- reduction

a Hold carfilzomib treatment; do at least weekly CBC with differential until toxicity resolves (ANC recovery $\geq 1.0 \times 10^{9}$ /L and platelets $\geq 75 \times 10^{9}$ /L).

b Re-treatment criteria = ANC recovery $\geq 1.0 \text{ x } 10^{9}/\text{L}$ and platelets $\geq 75 \text{ x } 10^{9}/\text{L}$.

c Patients who require a treatment delay of more than 3 weeks due to treatment-related toxicity will be discontinued from study treatment, unless the treating physician and the Study Chair agree that continued treatment at lower doses is in the best interest of the patient.

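### Table 3's thrombocytopenia rows end the hold at a grade that means platelets of 50 x 10^9/L, its footnotes require 75, and the Grade 3 seven-day dose rule inherits both values

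*Combined protocol and SAP*

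**What the plan says.** Section 6.1, Table 3 has four thrombocytopenia rows. Three of them (Grade 3, Grade 4, and recurrence after the initial reduction) end the hold with the same instruction: "Interrupt study treatment until toxicity reduced to \leq Grade 2 ^a". The fourth row is discontinuation. The Grade 3 band is printed as "Grade 3 (25 - <50 x 10" (to the ninth per litre), and Grade 4 lies below 25.

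The marker on that instruction leads to footnote a, which keeps the hold and the weekly counts going "until toxicity resolves (ANC recovery $\ge 1.0 \times 10^{9}$ /L and platelets $\ge 75 \times 10^{9}$ /L". Footnote b reads "Re-treatment criteria = ANC recovery $\geq 1.0 \times 10^9$ /L and platelets $\geq 75 \times 10^9$ /L". Both footnotes are reprinted under the continued table, again with "platelets $\geq 75 \text{ x } 10^{9}/\text{L".

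Step 2 of the Grade 3 row sets the restart dose. If the toxicity improves within 7 days, the instruction is "maintain same dose, if > 7 days reduce dose 1 level". It names no platelet value.

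The text of Section 6.1 says to "hold all study drugs and re-evaluate in 1 week", and that "Dose modifications on Day 1 of each cycle will be based on blood counts determined on the day of scheduled treatment". It takes a patient off study when platelets have not recovered in 3 weeks, again without a value. Section 6 makes every dose reduction permanent, allows two at most, and ends participation after a toxicity delay of more than 21 days. Footnote c also stops treatment after more than 3 weeks, unless the treating physician and the Study Chair agree to continue at a lower dose.

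**The concern.** The row and its footnotes print two platelet values for the end of one hold. A site that works from the grade in the row can re-dose after Grade 3 or 4 thrombocytopenia at counts of 50 to <75 x 10^9/L, below the protocol's own re-treatment limit.

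A site that follows the footnotes restarts at 75 but still has to choose a dose after a first Grade 3 event. The seven-day rule most naturally points back to the endpoint of step 1. That endpoint carries 50 by its grade and 75 by its footnote. The choice decides a reduction that cannot be reversed and that uses one of the two allowed.

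This is a multi-site study with toxicity among its secondary objectives. Dosing that depends on how a site reads the table would therefore affect both patient safety and the comparability of the safety data.

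**Working it through.** The plan states no figure on this point to reproduce. The check sets the thresholds side by side and follows them through the dosing rules.

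**Inputs**
- Grade 3 thrombocytopenia: 25 to <50 x 10^9/L (Table 3). The table prints no Grade 2 band, so Grade 2 or better is inferred as at least 50.
- Footnotes a and b: at least 75 x 10^9/L.
- Dose levels: 56, 45 and 36 mg/m² (Table 2). A full cycle from Cycle 2 onwards has 6 doses (Table 1).
- Re-check at 1 week, then at least weekly (Section 6.1 and footnote a).

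**Step 1: where the two values disagree**

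| Platelets (x 10^9/L) | Row (at least 50) | Footnotes (at least 75) |
|---|---|---|
| 49 | hold | hold |
| 50, 60, 74 | hold ends | hold |
| 75, 90 | hold ends | hold ends |

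The gap is 75 - 50 = 25 x 10^9/L, and the disputed range is 50 to <75. For neutrophils, Grade 2 or better and the footnotes both mean at least 1.0 x 10^9/L. The neutropenia and febrile neutropenia rows are therefore consistent and not part of this point.

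**Step 2: restart dose after a first Grade 3 event.** The counts are assumed. A patient on 56 mg/m² in Cycle 2 or later has platelets of 45 on a scheduled Day 1, 60 at the 1-week re-check and 80 at 2 weeks. Starting from a Day 1 count keeps the Section 6.1 sentence on nadir counts out of play.
- Row grade alone: restart at 7 days. This is within the 7-day limit, so the dose is 56 mg/m².
- Footnotes, with improvement meaning at least 75: restart at 14 days. This is over 7 days, so the dose is 45 mg/m², permanently.
- Footnotes, with improvement meaning Grade 2 or better: restart at 14 days at 56 mg/m², because 60 was reached by day 7.

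At the 1-week re-check only counts of 50 to <75 separate the readings. Below 50 all of them hold; at 75 or more all of them restart at 56 mg/m².

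**Step 3: size of the dose difference**
- Per dose: 56 - 45 = 11 mg/m²; 11/56 = 19.6%.
- Per full cycle: 6 x 56 = 336; 6 x 45 = 270; 336 - 270 = 66 mg/m²; 66/336 = 19.6%.

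**Step 4: counts that stay in the disputed range.** Suppose platelets rise to 60 and stay there beyond 3 weeks. Under the row grade, treatment restarts in all three rows (at a reduced dose after a Grade 4 or recurrent event). Under the 75 reading the patient has not recovered and faces discontinuation under Section 6, Section 6.1 and footnote c, subject to footnote c's exception. For Grade 4 and recurrent events the restart dose is the same on either reading, but the consequence is not limited to restart timing.

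**The case against.** The strongest reply is that the table already settles restart. The marker sits on the phrase itself, footnote a gives 75, and footnote b is labelled as the re-treatment criterion. A count of 75 is also Grade 2 or better, so one action satisfies both statements. This stands. A reader might infer that the protocol leaves restart open between 50 and 75, or permits re-dosing at 50. It does neither once the footnotes are read; the row simply shows the wrong figure to someone who stops at the grade.

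A reader might also infer that the seven-day rule is tied to no value at all. That goes too far. It is the second of two numbered steps, and the natural reference is the endpoint of the first. The difficulty is that this endpoint carries two values. Even readers who accept 75 for restart can differ on whether reaching Grade 2 within 7 days preserves the dose. Keeping the dose on Grade 2 within 7 days while restarting at 75 is a coherent rule, and the sponsor may intend it.

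Section 5.1.1 requires changes outside the 2-day window to be discussed with the Medical Monitor. If that applies, a central reader sees such cases. It is a useful safeguard, but it gives the monitor no platelet value to apply.

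Finally, the worked case uses counts chosen to fall in the gap, and 19.6% is just one step of Table 2. Both remarks are fair. In the text as extracted, footnotes b and c show no anchor in the table; that may be a conversion artefact, and nothing here rests on it.

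**Conclusion.** The point holds and should be fixed. Three thrombocytopenia rows print a grade equivalent to 50 x 10^9/L where the governing footnotes require 75. For restart, the full text supports 75. For the dose after a first Grade 3 event, the text does not decide between 56 and a permanent 45 mg/m² when the 1-week count is 50 to <75; the difference is 66 mg/m² per full cycle (-19.6%). For all three rows, a count that stays in that range past 3 weeks separates restart from possible discontinuation.

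This rests on two things: inferring 50 from the upper limit of the printed Grade 3 band, and the assumed platelet counts in the worked case. The documents give no rate of Grade 3 or 4 thrombocytopenia, so the number of patients affected cannot be estimated.

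A reader might infer that the primary analysis is compromised. The documents do not support that: the Simon design (23, then 56, accrual 62) and the efficacy analysis rules make no use of these thresholds.

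**What to change.** By amendment to Section 6.1:

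1. In the Grade 3, Grade 4 and first-recurrence thrombocytopenia rows, replace the grade with *platelets ≥75 x 10^9/L*, matching footnotes a and b.
2. State that platelet recovery in the 3-week rule means the same value.
3. State which platelet value counts as improvement in the Grade 3 seven-day rule. The default is 75. If the clinical team intends it, Grade 2 or better within 7 days with restart at 75 is an acceptable alternative, provided it is written out.

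The neutropenia and febrile neutropenia rows need no change.

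The cost is wording only: no new tests, no added patients, and no change to the Simon design. Compared with acting on the row grade, using 75 means longer holds for patients at 50 to <75 and possibly some discontinuations when counts stay there past 3 weeks. If 75 also defines improvement, some first Grade 3 events will take a permanent one-level reduction that they would otherwise avoid; the alternative in item 3 spares those who reach Grade 2 within 7 days.
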